7 STUDY PARAMETERS

7.1 Efficacy Measures and Endpoints

7.1.1 Primary Efficacy Measure(s)

Part 1 and Part 2:

- Subject-reported ocular dryness score
- Fluorescein nasal region score

7.1.2 Co-Primary Efficacy Endpoints

Part 1 and Part 2:

• The co-primary symptom endpoint is the overall mean change from baseline in subject-reported ocular dryness score assessed using from Week 2 to Week 12. The population used for analysis of ocular dryness score will be subjects who have a baseline ocular dryness score

• The co-primary sign endpoint is the overall mean change from baseline in fluorescein nasal region score assessed using a from Week 2 to Week

12. The population used for analysis of fluorescein nasal region score will be subjects who have a baseline (Day 1) fluorescein nasal region

Part 2:

Burning/Stinging, Itching, Foreign Body Sensation, Eye Discomfort, Photophobia, and
Pain Score

7.1.5 Secondary Efficacy Endpoint(s)

The secondary efficacy endpoints are changes from baseline at weeks 1, 2, 4, 6, 8, 10 and 12 for each secondary efficacy measure, where available.

7.1.6 Criteria for Effectiveness

Co-primary Endpoint Efficacy Analysis:

• The co-primary symptom endpoint will be achieved in either Part 1 or Part 2 if the overall mean change from baseline in subject-reported ocular dryness score

assessed using l

from Week 2 to Week 12, in reproxalap-treated subjects is statistically significantly lower than that of vehicle-treated subjects in the corresponding vehicle arm. The population used for analysis of ocular dryness score will be

7.2 Safety Measures

- Visual acuity at distance utilizing an ETDRS chart
- Slit-lamp evaluation
- Adverse event query (reported, elicited and observed)
- IOP
- Dilated fundoscopy

8 STUDY MATERIALS

8.1 **Study Treatment(s)**

- 8.1.1 Study Treatment(s)/ Formulation(s):
 - Reproxalap 0.25% Ophthalmic Solution (reproxalap)
 - Vehicle Ophthalmic Solution (vehicle)
- 8.1.2 Description of and Justification for the Route of Administration, Dosage, Dosage Regimen, and Treatment Period(s):

Topical ophthalmic dosing is the optimal route of administration for DED treatment. The dosage and dosage regimen were selected based on nonclinical and clinical studies described in Section 2. The proposed treatment period of 12 weeks is based on the Phase 2 clinical trials and on the anti-inflammatory mechanism of action of reproxalap.

8.1.3 Instructions for Use and Administration

- At the study site, all Investigational Product (IP) must be stored under the conditions specified in the Investigator's Brochure in a secure area accessible only to the designated qualified clinical site personnel. All IP must be stored, inventoried and the inventories carefully and accurately documented according to applicable state, federal and local regulations, International Council on Harmonisation (ICH) Good Clinical Practices (GCPs) and study procedures.
- Subjects in the all OID treatment regimen (Part 1, arms A1 and A2) will receive
- Subjects in the all QID treatment regimen (Part 1, arms A1 and A2) will receive five treatment kits; subjects in the QID to BID treatment regimen (Part 1, arms B1 and B2) will receive four treatment kits.
- At a minimum, the immediate or secondary study drug packaging will provide the following information: study Sponsor identification, directions for use, required storage conditions, caution statements (including "New Drug–Limited by Federal Law to Investigational Use" language), and study identification.

8.2 **Other Study Supplies**

Other study supplies include urine pregnancy tests, Schirmer's test strips, sodium fluorescein, lissamine green, Fluress, Tropicamide, VAS rulers, and Tear Osmolarity cards.

9 STUDY METHODS AND PROCEDURES

9.1 **Subject Entry Procedures**

9.1.1 Overview

Subjects as defined by the criteria in sections 6.3, 6.4, and 6.5 will be considered for entry into this study.

9.1.2 Informed Consent

Prior to a subject's participation in the trial (i.e., changes in a subject's medical treatment and/or study related procedures), the study will be discussed with each subject, and subjects wishing to participate must give written informed consent (and/or assent) using an informed consent form. The informed consent form must be the most recent version that has received approval/favorable review by a properly constituted Institutional Review Board (IRB)/Independent Ethics Committee (IEC).

9.1.3 Washout Intervals

Prohibited medications, treatments, and activities are outlined in the exclusion criteria (Section 6.4).

9.1.4 Procedures for Final Study Entry

Subjects must meet all inclusion and none of the exclusion criteria.

9.1.5 Methods for Assignment to Treatment Groups:

Before the initiation of study run-in at Visit 1, each subject who provides written and informed consent will be assigned to a screening number. All screening numbers will be assigned in strict numerical sequence at a site and no numbers will be skipped or omitted. Each subject who meets all the inclusion and none of the exclusion criteria at Visit 1 and Visit 2 will be assigned a randomization number at the end of Visit 2. The Interactive Web Response System (IWRS) will be used to assign all randomization numbers.

Subjects are to be stratified by Visit 2 (Baseline) Pre-CAE ocular dryness score (on the Ocular Discomfort & 4-Symptom Questionnaire) and Visit 2 (Baseline) Pre-CAE

Randomization will continue until the sample size for the co-primary analysis described in Section 11.3 has been achieved.

Randomization and kit numbers will be assigned automatically to each subject as they are entered into the IWRS.

The site staff will dispense kit(s) required until the next visit. Both the randomization number and the dispensed study drug kit number(s) will be recorded on the subject's source document and electronic case report form (eCRF). The Sponsor, investigators, and study staff will be masked during the randomization process and throughout the study to study drug treatment assignment but not dosing regimen. The dosing regimen will be indicated with a leading alphabetical notation with each randomization number of either Q-Q (Part 1, arms A1 and A2) or Q-B (Part 1, arms B1 and B2).

9.2 **Concurrent Therapies**

The use of any concurrent medication, prescription or over-the-counter, is to be recorded on the subject's source document and corresponding case report form (CRF) along with the reason the medication was taken.

Concurrent enrollment in another investigational drug or medical device study is not permitted.

9.2.1 Prohibited Medications/Treatments

Disallowed medications/treatments during the study are outlined in the Exclusion Criteria (Section 6.4).

Confidential

9.2.2 Escape Medications

No escape medications are required for this study.

9.2.3 Special Diet or Activities

No special diets or activities are required for this study.

9.3 Examination Procedures

9.3.1 Procedures to be Performed at Each Study Visit with Regard to Study Objective(s)

Procedures listed below should be performed in the given order. See Appendix 3 (Section14.1) for details on methodologies and grading systems.

9.3.2	Visit 1: Day $-14 \pm 2 -$

All subjects

Pre-CAE[®]

- Informed Consent/HIPAA
- Demographic Data and Medical/Medication/Ocular History
- Review of Inclusion/Exclusion Criteria
- Urine Pregnancy Test (for females of childbearing potential): Women of childbearing potential must have a negative urine pregnancy test to continue in the study
- Multi-symptom Visual Analogue Scale (VAS)
- OSDI[©] (Part 1 only)
- BCVA Utilizing an ETDRS Chart
- Slit Lamp Biomicroscopy
- TFBUT (Part 1 only)
- Fluorescein Staining (corneal and conjunctival)
- Lissamine Green Staining (corneal and conjunctival)
- At least 15-minute wait between lissamine green staining and Schirmer's test
- Schirmer's test (Part 1 only)
- At least 15 minute wait between Schirmer's test and

- 90-minute
- Slit Lamp Biomicroscopy
- TFBUT (Part 1 only)
- Fluorescein Staining
- Lissamine Green Staining
- IOP
- Dilated Fundoscopy
- Review of Inclusion/Exclusion Criteria
- Run-in Instillation at the Study Site: All subjects having a positive response (as defined above) and meeting all other screening eligibility criteria at the end of Visit 1 will receive run-in drops for dosing. Qualified subjects will self-administer their initial run-in dose bilaterally at the study site under the supervision of a trained technician.
- Run-in Dispensation: Prior to discharge from the study site on Day -14, subjects will be dispensed sufficient Run-in supply to last until Visit 2 and will be educated on self-administration of vehicle run-in. Subjects will be instructed to self-administer one drop QID in each eye until Visit 2. Subjects will be instructed NOT to instill run-in on the morning of their next scheduled study visit (Visit 2).
- AE Query
- Subjects will be scheduled for Visit 2.

9.3.3 Visit 2: Day 1 -

- Study Run-in Collection
- Review of Inclusion/Exclusion Criteria
- Medical/medication history update
- AE query
- Multi-symptom Visual Analogue Scale (VAS)

- •
- BCVA Utilizing an ETDRS Chart
- Slit Lamp Biomicroscopy

• At least 15-minute wait between lissamine green staining and Schirmer's test

•	Run-in dosing 15-20 minutes
•	
•	Slit Lamp Biomicroscopy

- Review of Inclusion/Exclusion Criteria
- Randomization
- Study Drug Instillation at the Study Site: All subjects having a positive response (as defined above) and meeting all other screening eligibility criteria at the end of Visit 2 will be randomized to one of two treatment groups utilizing the IWRS system. Randomized subjects will self-administer their initial study drug dose bilaterally at the study site under supervision of a trained technician. Subjects will be instructed to dose four times a day (QID) in both eyes until their next visit.
- Study Drug Dispensation: Prior to discharge from the study site on Visit 2 (Day 1), randomized subjects will be educated on self-administration of study drug. Subjects will receive their assigned study drug kit with sufficient supply to last until Visit 3 and will be instructed NOT to self-administer study drug on the morning of their next scheduled study visit (Visit 3).

- AE Query
- Subjects will be scheduled for Visit 3.

9.3.4 Visit 3 (Day 8 ± 2)

- Study Drug Collection
- Medical/medication history update
- AE query
- Multi-symptom Visual Analogue Scale (VAS)

Slit Lamp Biomicroscopy

- Study Drug Dispensation: Prior to discharge from the study site on Visit 3, subjects will be re-dispensed the remaining unused ampules from their previous kit for athome dosing up to Visit 4. Subjects will be reinstructed to dose four times a day (QID) in both eyes until their next visit.
- Subjects will again be educated on self-administration of study drug. Subjects will be instructed to NOT self-administer study drug on the morning of their next scheduled study visit (Visit 4)
- AE Query
- Subjects will be scheduled for Visit 4.

9.3.5 Visit 4 (Day 15 ± 2)

- Study Drug Collection
- Medical/medication history update
- AE query

• Multi-symptom Visual Analogue Scale (VAS)

- Study Drug Dispensation: Prior to discharge from the study site on Visit 4, subjects will be assigned a new study drug kit via the IWRS and will also be re-dispensed the remaining unused ampules from their previous kit for at-home dosing up to Visit 5. Subjects will be reinstructed to dose four times a day (QID) in both eyes until their next visit.
- Subjects will again be educated on self-administration of study drug. Subjects will be instructed to NOT self-administer study drug on the morning of their next scheduled study visit (Visit 5)
- AE Query
- Subjects will be scheduled for Visit 5.

9.3.6 Visit 5 (Day 29 ± 2)

- Study Drug Collection
- Medical/medication history update
- AE query
- Multi-symptom Visual Analogue Scale (VAS)

- BCVA Utilizing an ETDRS Chart
- Slit Lamp Biomicroscopy

- Study Drug Dispensation: Prior to discharge from the study site on Visit 5, subjects will be assigned a new study drug kit(s) via the IWRS and will also be re-dispensed the remaining unused ampules from their previous kit for at-home dosing up to Visit 6. Depending on the assigned dosing regimen, subjects will be dispensed new kit(s) as follows:
 - Reproxalap/Placebo subjects in the all QID treatment regimen:
 - Subjects will continue to dose QID through the end of the treatment period
 - Subjects will be assigned two (2) kits at Visit 5
 - Reproxalap/Placebo subjects in the QID to BID treatment regimen:
 - Subjects will now be instructed to dose twice a day (BID) in each eye through the end of the treatment period
 - Subjects will be assigned one (1) kit at Visit 5
- Subjects will again be educated on self-administration of study drug. Subjects will be instructed to NOT self-administer study drug on the morning of their next scheduled study visit (Visit 6)
- AE Query
- Subjects will be scheduled for Visit 6.

9.3.7 Visit 6 (Day 43 ± 2)

- Study Drug Collection
- Medical/medication history update
- AE query
- Multi-symptom Visual Analogue Scale (VAS)
- •

- Study Drug Dispensation: Prior to discharge from the study site on Visit 6, subjects will be re-dispensed the remaining unused ampules from their previous kits for athome dosing up to Visit 7. Subjects will be reinstructed to dose either QID or BID based on their assigned treatment regimen in both eyes until their next visit.
- Subjects will again be educated on self-administration of study drug. Subjects will be instructed to NOT self-administer study drug on the morning of their next scheduled study visit (Visit 7)
- AE Query
- Subjects will be scheduled for Visit 7.

9.3.8 Visit 7 (Day 57 ± 3)

- Study Drug Collection
- Medical/medication history update
- AE query
- Multi-symptom Visual Analogue Scale

	_	
٠		
•	BCVA Utilizing an ETDRS Chart	

Slit Lamp Biomicroscopy

- Study Drug Dispensation: Prior to discharge from the study site on Visit 7, subjects
 will be assigned a new study drug kit via the IWRS and will also be re-dispensed the
 remaining unused ampules from their previous kit for at-home dosing up to Visit 8.
 Subjects will be reinstructed to dose QID or BID based on their assigned treatment
 regimen in both eyes until their next visit.
- Subjects will again be educated on self-administration of study drug. Subjects will be instructed to NOT self-administer study drug on the morning of their next scheduled study visit (Visit 8)
- AE Query
- Subjects will be scheduled for Visit 8.

9.3.9 Visit 8 (Day 71 ± 3)

- Study Drug Collection
- Medical/medication history update
- AE query
- Multi-symptom Visual Analogue Scale (VAS)

• Study Drug Dispensation: Prior to discharge from the study site on Visit 8, subjects will be re-dispensed the remaining unused ampules from their previous kit for athome dosing up to Visit 9. Subjects will be reinstructed to dose BID or QID based on their assigned treatment regimen in both eyes until their next visit.

- Subjects will again be educated on self-administration of study drug. Subjects will be instructed to NOT self-administer study drug on the morning of their next scheduled study visit (Visit 9)
- AE Query
- Subjects will be scheduled for Visit 9.

9.3.10 Visit 9 (Day 85 ± 3)

- Study Drug Collection
- Medical/medication history update
- AE query
- Urine Pregnancy Test (for females of childbearing potential): Women of childbearing potential must have a negative urine pregnancy test to continue in the study
- Multi-symptom Visual Analogue Scale (VAS)

•	
•	BCVA Utilizing an ETDRS Chart

Slit Lamp Biomicroscopy

- At least 15-minute wait between lissamine green staining and Schirmer's test
- AE Query
- IOP
- Dilated Fundoscopy
- Study Exit

9.3.11 Early Termination/Discontinuation

If a subject is discontinued from the study prior to Visit 9 (Day 85 ± 3), then all safety evaluations that are to be performed at Visit 9 should be performed on the day of discontinuation (early termination) or at the discretion of the investigator.

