In 1995, Augustin et al. (Augustin 1995) described elevations in tear MDA levels that correlated with severity in DED patients. Subsequently, Choi et al. (Choi 2016) reported that expression of MDA and 4-hydroxynonenal (another RASP commonly associated with inflammation) is increased in the tear film and ocular surface of patients with DED. Consistent with the literature that supports the notion that RASP mediate pro-inflammatory toxicity in DED, the anti-inflammatory effects of the RASP scavenger reproxalap have been demonstrated in Phase 2 clinical trials in DED, noninfectious anterior uveitis, and allergic conjunctivitis. In aggregate, a broad array of preclinical and clinical evidence supports the use of reproxalap for the treatment of ocular inflammation, including DED.

2 Clinical Studies of Reproxalap Ophthalmic Solution

Reproxalap ophthalmic solution is in clinical development for the treatment of ocular inflammation. The drug product, in various strengths, has completed a Phase 1 clinical trial, as well as a vehicle-controlled, double-masked Phase 2a clinical trial in allergic conjunctivitis; a vehicle-controlled, double-masked Phase 2b clinical trial in allergic conjunctivitis; a comparator-controlled, investigator-masked Phase 2 clinical trial in noninfectious anterior uveitis; a vehicle-controlled, double-masked Phase 2b clinical trial in DED; and a vehicle-controlled, double-masked Phase 2b clinical trial in DED. Phase 3 clinical trials in noninfectious anterior uveitis and allergic conjunctivitis are in progress. A total of 468 subjects have been exposed to topical ocular reproxalap in completed clinical trials.

In all clinical trials, no treatment-related serious adverse events (SAE) have been observed. Generally mild to moderate transient ocular stinging, lasting only up to a few

minutes, was reported in most subjects treated in the Phase 1 and the allergic conjunctivitis and dry eye disease Phase 2 clinical trials, and in a small proportion of subjects in the noninfectious anterior uveitis Phase 2 and the allergic conjunctivitis Phase 2b clinical trials. Table 1 summarizes the clinical exposure to topical ocular reproxalap for completed clinical trials.

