The Phase 2 clinical trials have demonstrated consistent activity of drug that is statistically superior to control, or, in the case of noninfectious anterior uveitis, the activity of reproxalap treatment, alone or in combination with Pred Forte[®], was statistically non-inferior to Pred Forte[®] (1% prednisolone acetate) monotherapy. Table 2 summarizes the outcomes of the completed clinical trials with topical ocular reproxalap.

A total of 51 subjects were randomized (17 per group). No SAEs were reported, and no clinically significant changes in visual acuity (VA), intraocular pressure (IOP), slit lamp biomicroscopic findings, or undilated funduscopic findings were observed. Eye drop comfort scores were highest in the 0.1% formulation, which was advanced to Phase 2b

Confidential

clinical testing. Most adverse events (AEs) were reported by subjects treated with the 0.5% formulations, and 11/12 subjects discontinued as a result of transient ocular irritation following instillation (1 subject in the 0.1% group, five in the 0.5% group, and six in the 0.5% lipid group).

Statistically significant improvement from baseline was observed across a broad array of DED signs and symptoms.

ADX-102-DED-009 was a multi-center, double-masked, vehicle-controlled clinical trial designed to assess the safety and activity of two concentrations of reproxalap (0.25% and 0.1%) administered four times daily (QID) to DED patients. Three hundred male and female subjects at least 18 years of age with a subject-reported history of DED in both eyes and meeting all other eligibility criteria were randomized in a 1:1:1 ratio to receive either topical ocular reproxalap (0.25%), reproxalap (0.1%), or vehicle.

Both concentrations of reproxalap demonstrated statistically significant and clinically relevant improvements from baseline and versus vehicle across multiple DED signs and symptoms. Figure 1 illustrates the broad pattern of activity on DED signs and symptoms of reproxalap 0.25% compared to vehicle in terms of improvement from baseline effect size at Week 12.

Statistically significant improvements over baseline as measured by the (severity) questionnaire (severity) questionnaire was evident as early as at Week 2. By Week 12, the 0.25% concentration was statistically superior to vehicle in change from baseline in overall ocular discomfort, dryness, and

stinging as measured by the

Figure 2 illustrates ocular dryness symptom score changes from baseline from Week 2 to Week 12.

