5 OVERALL STUDY DESIGN

The clinical trial is an adaptive Phase 3, multi-center, randomized, double-masked, parallel-group, vehicle-controlled design with block enrollment, and is comprised of two parts (Part 1 and Part 2). Test article will be self-administered topically to the eye.

Screening

Prior to randomization into either Part 1 or Part 2, subjects will receive 14 consecutive days (± 2) of vehicle, self-administered QID in both eyes, between Visits 1 and 2. Subjects randomized in Part 1 will not be eligible to participate in Part 2.

During the screening period (Visit 1 to Visit 2), two 90-minute exposures in the CAE[®] will be conducted to ascertain eligibility. Subjects who qualify will be randomized to receive study drug in a double-masked fashion for 84 days. At Visits 3 - 9, no CAE[®] exposure will occur but signs and symptoms will be assessed.

Part 1

Subjects will be randomized 1:1:1:1 into one of four treatment arms (100 subjects per arm):

A1. Reproxalap administered QID for twelve weeks

A2. Vehicle administered QID for twelve weeks

B1. Reproxalap administered QID for four weeks, followed by BID administration for eight weeks

B2. Vehicle administered QID for four weeks, followed by BID administration for eight weeks

The results of A1 will be compared to the results of A2. The results of B1 will be compared to the results of B2.

Subjects, the Sponsor, the CRO, investigators, and site personnel will be masked to treatment assignment. Subjects will not be masked to dosing regimen.

The total number of expected participants in Part 1, including screen failures, is approximately 1,000 subjects. The duration of Part 1 is approximately 14 weeks (98 days), including 12 weeks of treatment.

Part 2

Subjects will be randomized 1:1 to receive treatment with either reproxalap or vehicle for twelve weeks. Dosing regimen and subject number per arm will be determined based on the results of Part 1. The duration of Part 2 is approximately 14 weeks (98 days), including 12 weeks of treatment.

Subjects, the Sponsor, the CRO, investigators, and site personnel will be masked to treatment assignment.

Subjects who terminate early during the treatment period will be asked to complete safety assessments prior to commencement of alternative DED therapy (if possible). Subjects who are terminated early from the study will not be replaced.

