13.1.1 OCULAR DRYNESS SCORE

Subjects will be asked to subjectively rate ocular dryness (both eyes [OU]) by placing a vertical mark on the horizontal line to indicate the level of discomfort. The length of the assessment line is 100 mm; a measure of 0 mm corresponds to "No Discomfort" and 100 mm corresponds to "Maximal Discomfort."

Ocular dryness score (0-100 VAS) will be summarized for Visit 3 (Day 8) to Visit 9 (Day 85) by treatment arms using continuous descriptive statistics. Overall mean change from baseline from week 2 to week 12 for each treatment arm in ocular dryness score will be compared between active treatment and vehicle. The primary analysis will use an MMRM adjusted for baseline ocular dryness score (0-100 VAS), treatment arm, visit, and the interaction of treatment arm and visit as fixed effects and subject as the random effect. Least squares (LS) means for each treatment arm and the LS mean difference between treatment arms for the overall mean change from baseline from week 2 to week 12 and change from baseline for each visit will be presented from the model together with standard errors (SE), two-sided p-values, and two-sided 95% CIs. Primary analysis will be performed on the ITTOD population with observed data only.

31/OCT/2019

All post-baseline data from the two treatment groups will be included in the models. Comparisons between two treatment arms (e.g., between reproxalap Q-Q and vehicle Q-Q) for overall mean change from baseline from week 2 to week 12 and change from baseline at a given visit will be obtained by comparing the corresponding LS mean estimates.

Change from baseline will also be analyzed using analysis of covariance (ANCOVA) models adjusted for baseline ocular dryness score and treatment arm. Two-sample t-tests and Wilcoxon rank sum tests will be used as sensitivity analyses. Cohen's d effect size will be reported for differences in change from baseline between treatment arms.

Markov chain Monte Carlo (MCMC) imputation with the ITTOD population will used for the sensitivity analysis under MAR assumption. A single imputation will first impute non-monotone missing data using MCMC to obtain a dataset with a monotone missing pattern. Then, MCMC will be used to perform twenty imputations from the dataset with monotone missingness. The primary endpoint will be re-analyzed to confirm the results from the primary analysis.

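### Early-termination visits require safety evaluations only, so nothing ensures that the two co-primary scores are taken at exit or placed in the analysis

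*Protocol*

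**What the plan says.** Protocol 9.3.11 requires that "all safety evaluations that are to be performed at Visit 9 should be performed on the day of discontinuation", or at the investigator's discretion. Section 5 gives the same scope: "Subjects who terminate early during the treatment period will be asked to complete safety assessments prior to commencement of alternative DED therapy", where possible. It adds that leavers are not replaced.

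Protocol 7.2 lists the safety measures, beginning with "Visual acuity at distance utilizing an ETDRS chart" and continuing with slit lamp, adverse event query, IOP and dilated fundoscopy. Protocol 7.1.1 places "Subject-reported ocular dryness score" and the fluorescein nasal region score under primary efficacy.

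The SAP's Part 1 schedule (3.2) has no early-termination column, and the SAP has no rule for assigning an exit value to a visit. For dryness, SAP 13.1.1 states that "Primary analysis will be performed on the ITTOD population with observed data only", with all post-baseline data in the model; 13.1.2 does the same for staining in ITTFSN. Both sections add multiple imputation under MAR and a control-based pattern mixture model. SAP 8.2 says that such imputation may be done, where 13.1.1 and 13.1.2 say that it will be.

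**The concern.** An early leaver who attends is already having visual acuity, slit lamp, IOP and fundus examinations. The VAS and fluorescein staining are done at every scheduled visit, yet the plan does not ask for them at this one. No efficacy follow-up after discontinuation is described, so this is the last chance to observe either co-primary measure.

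A likelihood analysis under MAR predicts a leaver's missing visits from that subject's observed values and from subjects who stayed. If leavers are doing worse when they go than their last scheduled visit showed, the prediction is too favourable. If this happens mainly on active drug, the estimate favours reproxalap. A subject who leaves before Visit 3 with no exit score contributes nothing to the primary model.

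The effect would reach beyond Part 1, because its estimated differences, SDs and correlations size Part 2 and its results choose the Part 2 regimen.

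Tolerability-related exit is plausible. Protocol Section 2 says that transient stinging "was reported in most subjects treated in the Phase 1 and the allergic conjunctivitis and dry eye disease Phase 2 clinical trials".

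**Working it through.** **Inputs.** From SAP Section 5: dryness difference 0.3952, SD 0.73, correlation ρ = 0.7783; staining difference 0.2967, SD 0.53, ρ = 0.5749; four repeated measures assumed, six planned. From SAP 3.1: post-baseline visits on Days 8, 15, 29, 43, 57, 71 and 85, so six visits fall in Weeks 2–12. The dropout rate is not stated; I assume 10% and 20% on active and none on vehicle.

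**The plan's own figure.** With AR(1) correlation, the variance factor for the mean of four measures is f = (1/16) Σᵢⱼ ρ^|i−j|, which is 0.572 for staining and 0.752 for dryness. Then n per arm = 2·SD²·f·(1.960 + 1.282)²/Δ².

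- Staining: 2 × 0.2809 × 0.572 × 10.51 / 0.0880 = 38.4, so 39.
- Dryness: 2 × 0.5329 × 0.752 × 10.51 / 0.1562 = 53.9, so 54.

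Both match the SAP, so AR(1) is used below. Neither figure includes a dropout allowance.

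**Bias formula.** Let p be the share of the active arm that leaves and M the number of the six averaged visits missed. Completers have the full effect Δ; leavers have none from some point on. If a leaver's last observed score already shows no benefit, the model carries a fraction ρ^h of that deficit to the h-th missed visit. The bias as a share of Δ is

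(p/6) × S(M), where S(M) = Σ (1 − ρ^h) for h = 1 to M.

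If the last observed score still shows the full effect, no deficit is carried and the bias is (p/6) × M. An exit score showing no benefit fills one missed visit, leaving (p/6) × S(M − 1). Under AR(1) only the last observed value matters, so including Week 1 in the model changes nothing.

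| | S(2) | S(3) | S(4) |
|---|---|---|---|
| Dryness | 0.616 | 1.144 | 1.778 |
| Staining | 1.095 | 1.905 | 2.795 |

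**Case A: leavers never benefited.**

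| p, M | Dryness | Dryness with exit score | Staining | Staining with exit score |
|---|---|---|---|---|
| 10%, 3 | 1.9% | 1.0% | 3.2% | 1.8% |
| 20%, 4 | 5.9% | 3.8% | 9.3% | 6.3% |

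**Case B: full benefit at the first analysed visit, none afterwards (M = 5).**

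| p | Either endpoint, no exit score | Dryness with exit score | Staining with exit score |
|---|---|---|---|
| 10% | 8.3% | 3.0% | 4.7% |
| 20% | 16.7% | 5.9% | 9.3% |

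The share removed in Case B is 1 − 1.778/5 = 64% for dryness and 1 − 2.795/5 = 44% for staining, or about 65% and 45%. A large-sample simulation of Case B at 10% dropout agrees: bias 0.033 for dryness (0.033/0.3952 = 8%) and 0.024 for staining (0.024/0.2967 = 8%).

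**Units.** The dryness endpoint is a 0–100 VAS. A difference of 0.3952 with SD 0.73 does not look like that scale, and Protocol Section 2 gives the earlier trial's dryness score a range of 0 to 5. The bias is therefore given only as a percentage of the planned effect.

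**The case against.** The strongest reply is that the plan already handles much of this. Visits before exit stay in the model, scheduled visits are at most 14 planned days apart, and the control-based analysis addresses informative dropout. This stands in part. It is why the Case A bias is small, and why multiplying dropout by the fraction of visits missed (0.10 × 0.5 = 5%; 0.20 × 0.67 = 13%) is the wrong calculation for that case: it credits every leaver with the full effect whatever was seen earlier. Imputation, however, starts from the observed data and cannot supply the exit score.

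Three stronger readings are tempting, and the documents do not support them.

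- A reader might infer that exit scores are excluded. They are not: 9.3.11 leaves room for discretion, 9.4.2 allows other assessments at unscheduled visits, and a subject who stops at a scheduled visit may already have completed the VAS. The gap is that nothing ensures collection or use.
- A reader might infer that irritation on active drug drives dropout here. The statement that "11/12 subjects discontinued as a result of transient ocular irritation" comes from a 51-subject trial of 0.1%, 0.5% and 0.5% lipid formulations with no vehicle group listed. Its bracketed counts (1 + 5 + 6) sum to 12, and 11 of those are on the 0.5% strengths. No discontinuation reasons are given for 0.25%, and Section 2 reports no evident safety concerns in the trial of 0.1% and 0.25%. Differential exit is a risk to plan for, not a documented fact.
- A reader might infer that an exit score would cure the problem. It helps most when benefit disappears between the last visit and exit. Benefit lost after drops are stopped would not show on the exit day, and subjects lost to follow-up have no exit visit.

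**Conclusion.** The gap is real: two protocol sections limit the required exit assessment to safety, and the SAP neither schedules nor places an exit value for either co-primary measure. I read the SAP's Part 1 schedule; the protocol's appendix schedules were not available to me, so Part 2 is unchecked on this point.

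The size is modest and conditional. With 10–20% active-arm dropout and complete vehicle follow-up, the estimate is too favourable by about 2–6% of the planned effect for dryness (1–4% with an exit score) and 3–9% for staining (2–6%) if leavers never benefited. It is about 8–17% if benefit vanishes right after the first analysed visit, which is close to a worst case for leavers with one analysed visit. The direction depends on leavers doing worse than those who stay and on more exits from active than from vehicle; similar dropout on vehicle would change the figures.

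This is an inexpensive improvement worth making. It does not by itself put the primary analysis in doubt.

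**What to change.** **Protocol 9.3.11 and Section 5.** Require the multi-symptom VAS and fluorescein staining at the early-termination visit where the subject attends, if possible before alternative therapy. Keep the usual order: VAS first, then visual acuity, slit lamp and staining. Moving staining to the front would conflict with Protocol 9.3.2 and SAP 15.2, which put visual acuity before the slit lamp.

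**SAP.** Assign the exit value to the next scheduled visit not yet attended, or to the nearest unoccupied visit within a stated window, and include it in the MMRM and both imputation models. A plain nearest-visit rule can collide with a visit already attended: an exit on Day 10 is nearest to Visit 3, which may have been done on Day 8. Make 8.2 agree with 13.1.1 and 13.1.2 that the imputation analyses will be run. The Part 2 SAP is to be finalized after Part 1 database lock, so the rule can be adopted there alongside a protocol amendment.

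**Cost.** Protocol and SAP wording, and a few minutes per leaver with assessments already in use. Exit scores may not follow the instruction to skip the morning dose before a scheduled visit, so the time of the last dose should be recorded. Some bias remains; continued efficacy follow-up after drops are stopped would address more of it, at a higher cost.
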